9.0 Statistical Considerations

9.1 Primary objective.

The primary objective of this pilot study is to evaluate the histologic result of treating primary lung cancer or solitary metastatic lung cancer after PTC. The primary statistical objective is to estimate the PTC success rate (p) as defined in Section 3.4, paragraph 6, i.e., that > 75% of the tissue analyzed histologically 3 weeks post-PTC is negative for cancer. The pilot study hypothesis is that all tumor will be eradicated via PTC.

9.2 Sample size.

The target sample size for this pilot study is 10 evaluable patients (defined in Section 7.5) , from Cohorts A and B combined. The 2 cohorts are defined in Section 2.0, and will not be distinguished in this small pilot study. It is expected that most (if not all) patients who enroll will be in Cohort A. Both point and 80% confidence interval (CI) estimates of p , and of the mean % of tissue which is found negative for cancer (TNC) histologically will be calculated. The precision (i.e, half-width of the CI) attainable in the estimate of (p) with $N=10$ evaluable patients will depend on the point estimate of the sample rate (p), in the following manner:

Rate	0.10	0.20	0.30	0.40	0.50	0.60	0.70	0.80	0.90
Precision	0.126	0.156	0.175	0.185	0.188	0.185	0.175	0.156	0.126

With 10 evaluable patients, (p) could be estimated to a precision of 0.188 or better (i.e., smaller) for most values of (p), with 80% confidence. The table values were computed using Wilson 80% confidence intervals in the PASS 2011 software program "Confidence Intervals for One Proportion – New". With 10 evaluable patients, the mean of a continuous endpoint (e.g., the mean % TNC) could be estimated to within 0.437 standard deviation (SD) units, with 80% confidence. Those are reasonable precision and confidence levels for a small pilot study, and should provide sufficiently precise estimates for use in planning a subsequent investigation.

9.3 Secondary objectives.

The secondary objectives are: 1) to provide a qualitative assessment of the histology from the ablation and tumor margins; and 2) to perform various correlative studies described in Section 7.0. Secondary objective (1) will not likely require statistical assessment. For secondary objective (2), summary statistics will be calculated, including point and interval estimates of either means or proportions as appropriate, for: PET SUVmean, PET SUVmax, (clinical CT) response rate (RR), and pathologic response rate (pRR). As per Section 7 (and its Study Calendar), the post-PTC CT results will be obtained at 3 weeks and at 6 months; the post-PTC PET results only at 6 months.

9.4 Toxicity (Adverse Event) and Safety Evaluation.

There are various types of adverse events (AEs) listed in Section 6.0. Any one of them could occur as a serious AE (SAE). Based on our prior clinical experience with cryotherapy, we anticipate that up to 20% of patients may have such complications, but that would not be regarded as reason to stop the study.

However, to prevent continuation of this trial in the face of an unacceptably high rate of SAE's (combining all types), we would consider stopping the trial if we see an early example(s) of that.

In addition, as part of our Data and Safety Monitoring Plan for this trial, we have devised a statistical monitoring plan for SAEs. This approach uses a 1-sided upper 80% confidence limit (CL) to determine the first opportunity at which the observed SAE rate provides evidence that the true (and unknown) SAE rate could be > 30%.

Using this statistical monitoring plan, if 1 patient in the first 9 patients are treated and none have an SAE, then we can be 80% confident that the true (and unknown) SAE rate is < 30%, because that is the smallest sample size for which the 1-sided upper 80% CL (0.268) is still < 30%.

The first statistically-based early stopping opportunity for safety reasons occurs if 1 patient has an SAE among the first 8 (or fewer) patients treated, in which case the 1-sided upper 80% confidence limit (0.303) just exceeds 0.30. The second such early stopping opportunity for safety reasons occurs if 2 patients have an SAE among the first 10 (or fewer) patients treated, in which case the 1-sided upper 80% confidence limit (0.327) just exceeds 0.30. Over the full range of the 10 patients intended for this pilot protocol study, we would recommend re-evaluation of the study for safety reasons according to the statistical monitoring plan for toxicity given in Table 1.

Table 1. Statistical Monitoring Plan for Toxicity

We would recommend re-evaluation of the study for safety reasons if there were X many SAE's among the first N (or fewer) patients treated:

X	N	p	UCL
1	8	0.125	0.303
2	10	0.200	0.327

In Table 1, X = the cumulative number of SAE's observed thus far; N = the number of cryotherapy patients treated thus far; p = the observed (i.e., sample) SAE rate, combining SAE's of any type; and UCL = the exact 1-sided upper 80% binomial confidence limit for p.

9.5 Accrual rate, accrual duration, and study duration.

The expected accrual rate is 2 patients/year, hence it should take 60 months to enroll the intended 10 evaluable patients. Allowing for 6 months to obtain all endpoints for the last patient enrolled, the expected total duration of this pilot study is 66 months. It may require enrolling 12-15 patients in order to obtain 10 evaluable patients among them.

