1.0 SCHEMA

Prior to lung resection at three weeks after PTC, the patient will receive a dynamic enhanced (i.e., non-contrast, arterial and delayed phase) computed tomography(CT) of the chest. These preoperative studies will be compared with the histologic results from thoracotomy, obtained at least 2 days after PTC and no more than 2 months after PTC to assure thorough necrosis. Evaluations will include dimensions of the resected pathologic specimen's necrotic center and its peripheral rim, compared to the CT findings of vessel proximity, central cavitation and associated healing rim, noting the enhancement of the rim and overall ablation zone. The resected ablation zone will undergo histologic analyses of the tumor region near vasculature, as well as the anterior, posterior, superior, inferior, medial and lateral margins to determine if cancer is present and note the characteristics of the healing rim (e.g., inflammatory infiltrates). If cancer is present in any area, this will be compared to the similar ablation margin on CT to assess any differences in enhancement or nodularity.

Key Inclusion Criteria

1. The patient will be a candidate for a thoracotomy
2. The patient will have a peripheral lung tumor 3.0 cm or less in diameter
3. If primary lung cancer, non-invasive staging or mediastinoscopy will suggest the patient has Stage I disease. If patient has metastatic disease, the lungs will be the only site of metastases.
4. The patient will have a biopsy proven cancer before PTC and thoracotomy, including either a CT-guided needle biopsy diagnosis, a bronchoscopic or transbronchial biopsy.

Treatment Plan

1. The patient will undergo CT-guided PTC with the intent to eradicate the entire tumor(s).
3. The patient will have CXR at weeks 1 and 2 (± 2 days).
4. Approximately 3 weeks after PTC, (2-53 days) chest CT and pulmonary function tests will be performed within 7 days of planned resection.
5. Approximately 3 weeks after PTC (2-60 days) the patient will undergo a thoracotomy with resection of the treated lung, consisting of lobectomy for primary lung cancer or wedge resection with adequate margin for a metastatic lesion. The mediastinal lymph nodes will undergo dissection.
6. The resected ablation zone(s) will be measured and histologic samples taken from all six margins and resected lymph nodes.
7. The pathology results will be compared with the preoperative, post-cryotherapy CTs.

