2.0 OBJECTIVES

The primary objective of the study is to evaluate the histologic result of treating primary lung cancer or solitary metastatic lung cancer after PTC.

The secondary objective is to provide a qualitative assessment of the histology from the ablation and tumor margins, comparing histologic observations with imaging enhancement patterns by computed tomography (CT) before and after PTC. Post-cryotherapy, pre-surgical CT scan dimensions and characteristics (e.g., central necrosis and healing rim) will be qualitatively compared to similar areas of the surgical specimen. In addition, histology samples from anterior, posterior, superior, inferior, medial and lateral areas of the resected tumor will be compared to enhancement zones of the ablation margin for any residual cancer.

A tertiary objective is long term follow up for clinical outcome and overall survival.

A total of ten evaluable patients qualifying in either Cohort A or Cohort B will be included.

Cohort A. Patients who have been diagnosed with Stage I primary peripheral lung cancer less than 3.0 cm in average diameter without prior radiation or chemotherapy.

Cohort B. Patients with metastatic solitary or multiple (≤ 3) peripheral lung lesions less than 3.0 cm in average diameter which have not been treated with radiation or chemotherapy since the new metastatic lesion appeared.

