5.1 Concomitant Medication Therapy

Patients will be instructed to take Prednisone to prevent/alleviate any acute inflammation. The steroid should be taken:

20mg BID on the day of the cryotherapy procedure

20mg BID on the day after the procedure

20mg BID two days after the procedure

20mg AM and 10mg PM three days after the procedure

10mg AM and 10mg PM four days after the procedure

10mg five days after the procedure

5mg six days after the procedure

STUDY CALENDAR

	Pre-Cryotherapy	Cryotherapy	Week 1 ^H	Week 2 ^H	Week 3	Thoracotomy ^J	Month 6
Diagnosis	X						
Informed Consent	X						
Demographics	X						
Medical History	X						
Physical Exam ^G	X ^C						
Chest X-ray	X ^B	X	X	X			
CT scan of chest	X ^B				X ^I		X
PET scan	X ^A						X
MRI of brain	X ^D						
Pulmonary Function Tests (PFTs)	X ^D				X ^I		
EKG	X ^D						
CBC w/differential	X ^C						
Chem-7 ^F , alkaline phosphatase, SGOT, bilirubin	X ^C						
INR	X ^E						
Pregnancy test, urine or serum	X ^E						
Histology						X	

B: Must be performed within 42 days of cryotherapy

C: Must be within 6 weeks of cryotherapy

D: Must be within 12 weeks of cryotherapy

E: Must be within 1 week of cryotherapy

F: Chem-7 includes BUN, creatinine, glucose, and electrolytes

G: Physical exam to include heart, rate, blood pressure, respiratory rate, temperature and documentation of concurrent medication

H: +/- 2 days

I: 2-53 days following percutaneous cryotherapy; within 7 days of planned thoracotomy

J: Less than 12 weeks from percutaneous cryotherapy

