7.4 Follow-Up

All patients who are registered to the trial will be followed for survival regardless of whether the patient completed protocol treatment.

[figure not shown]
[figure not shown]
All adverse events and serious adverse events that are related to protocol treatment will be followed until resolution.

7.5 Evaluable patients.

To be evaluable for this pilot study, the patient must undergo the planned thoracotomy < 12 weeks from percutaneous cryotherapy, as noted in the Study Calendar. Inevaluable patients will be replaced until the statistically required sample size of 10 evaluable patients (as determined in Section 9.2) has been obtained.

8.0 **Figure 1: The 1-2 rule for cryoprobe placements according to tumor size (black circles)**

Using a single cryoprobe requires precise central placement [22] to cover the tumor with ice (darker gray around each probe), let alone lethal ice (smaller dashed line ~5 mm inside ice). Conversely, when more probes are used, the sum of the individual ice projections (darker gray circles) synergistically expand, extending lethal ice (larger dashed line) ~ 5 mm beyond all tumor margins while visible ice (lighter gray circle) projects ~ 10 mm.

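### Section 9.3's only post-cryotherapy PET comes after the treated lung has been resected in every evaluable patient, so neither its SUV summaries nor the month-6 CT can describe the effect of treatment

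*Combined protocol and SAP*

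**What the plan says.** Section 9.3 gives two secondary objectives. The second is the set of correlative studies in Section 7.0, for which means or proportions are to be estimated with intervals for "PET SUVmean, PET SUVmax, (clinical CT) response rate (RR), and pathologic response rate (pRR". On timing, the same section states that "the post-PTC CT results will be obtained at 3 weeks and at 6 months; the post-PTC PET results only at 6 months". The Study Calendar agrees: PET before cryotherapy and at month 6; chest CT before cryotherapy, at week 3 and at month 6.

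The resection dates are set elsewhere. Schema item 5 reads "Approximately 3 weeks after PTC (2-60 days) the patient will undergo a thoracotomy with resection of the treated lung". Under Section 7.5, to be evaluable "the patient must undergo the planned thoracotomy < 12 weeks from percutaneous cryotherapy", and calendar note J gives the same limit: "Less than 12 weeks from percutaneous cryotherapy". Note I places the week-3 CT at "2-53 days following percutaneous cryotherapy; within 7 days of planned thoracotomy".

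Section 5.0 describes the six-month CT and PET as something patients are asked to have, for long-term follow-up. Section 9.3 does not repeat that description. Section 7.2 defines complete and partial CT response but names no assessment visit.

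**The concern.** Section 7.0 wants imaging that shows whether tumor remains after cryotherapy, because future patients who cannot be operated on will have only imaging to rely on. It names both CT and PET for this and defines SUV as uptake over a region of interest. Section 9.3 attaches its SUV summaries to that objective, but the only PET after PTC is taken when the treated lesion is no longer in the chest.

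An analyst who follows 9.3 as written would therefore produce post-PTC SUV estimates that describe resected patients after surgery. A low SUV would be expected because the tissue has been removed, whatever cryotherapy had achieved. The same holds for the month-6 CT if it enters the response rate. At stake is whether surgical clearance could be reported as an effect of PTC in a stated secondary analysis.

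**Working it through.** **The plan's own figure.** Section 9.3 gives no numbers. The nearest is in Section 9.2: with 10 patients, a continuous mean is estimated to within 0.437 SD at 80% confidence. The half-width is t(0.90, 9 df)/√10 = 1.383/3.162 = 0.437, so the figure is right. The difficulty is not precision but what a mean of ten month-6 SUVs would be a mean of.

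**Dates, counted from PTC**

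- Latest resection under the schema: day 60.
- Latest resection for an evaluable patient under 7.5 and note J: before day 84 (12 × 7), that is, day 83.
- Month 6: day 182 (26 × 7). The documents give no day count, so this is an assumption.
- Gap under the schema limit: 182 − 60 = 122 days or more.
- Gap under the 12-week limit: 182 − 84 = 98, so more than 98 days.

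If month 6 were counted from thoracotomy, the scans would follow resection by definition. The conclusion holds under either limit and either starting point.

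**What each scan can show in an evaluable patient**

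| Scan | Treated lesion in place? | Scans for N=10 |
|---|---|---|
| Baseline PET and CT | Yes, but before PTC | 10 of each |
| Week-3 CT (note I) | Yes | at most 10 |
| Month-6 CT | No | at most 10 |
| Month-6 PET | No | at most 10 |

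After PTC there are thus at most 20 CTs, of which at most 10 show the treated lesion, and at most 10 PETs, of which 0 do. The month-6 counts are maxima because Section 5.0 only requests those scans.

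**Patients outside the evaluable set.** Section 9.3 does not restrict its summaries to evaluable patients. Section 9.5 expects 12-15 enrolled for 10 evaluable, leaving 12 − 10 = 2 to 15 − 10 = 5 others. How many of these would be treated but never resected is not given; the assumed range is 0 to 5. Only they could have a month-6 PET with the treated lesion still present.

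**Which CT feeds RR.** Schema item 7 says "The pathology results will be compared with the preoperative, post-cryotherapy CTs". Section 2.0 bases the imaging comparison on "Post-cryotherapy, pre-surgical CT scan dimensions and characteristics". Section 7.0, which contains the response criteria, starts from the CT taken before the operation. All three point to the pre-resection CT, although for the comparison with pathology rather than for RR by name. What is missing for RR is mainly a cross-reference.

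**Windows, a separate matter.** Note I allows CT up to day 53 and within 7 days of the planned thoracotomy, so it can be met only for surgery planned by day 53 + 7 = 60. Section 7.5 and note J run to day 83. The passages disagree, but both limits precede month 6, so the PET point does not depend on them.

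**The case against.** The best reply is that 9.3 never says month-6 SUV measures the effect of PTC. It promises summary statistics and states when scans take place; it sets no criterion for SUV change or PET response. Section 5.0 already treats the six-month scans as long-term follow-up, which fits the tertiary objective. A baseline PET is required, so SUV summaries have some valid content. Section 7.0 itself warns that inflammation can produce false PET results and relies on histology for that reason. These are also descriptive summaries in a ten-patient pilot.

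Much of this stands. Baseline SUV can be reported, month-6 scans are legitimate surveillance, and without table shells one cannot say how the results would be labelled. It does not remove the point. Section 9.3 places the SUV summaries under the Section 7.0 objective, calls the month-6 scans post-PTC, and does not carry over the Section 5.0 description. Section 9.5 also allows six months for all endpoints of the last patient. A baseline SUV cannot stand in for a post-treatment one.

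Two stronger readings are tempting and should be resisted:

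- A reader might infer that RR would be read at month 6, so that surgical removal would score as complete response. Sections 1.0, 2.0 and 7.0 point to the pre-operative CT, so that reading is unlikely.
- A reader might infer that patients operated on between days 61 and 83 can have no CT that meets note I. Note I refers to the planned operation. Surgery planned by day 60 and then delayed can still have a compliant CT; the gap arises only if surgery is planned later than day 60, which the schema does not allow.

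**Conclusion.** The point holds for PET without qualification: 0 of at most 10 post-PTC PETs in evaluable patients can show the treated lesion, and the planned post-PTC SUV estimates cannot describe the effect of PTC in those patients. The month-6 CT cannot measure response to PTC in them either. For RR, what is missing is largely an explicit link to the pre-resection CT.

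The size in days rests on taking month 6 as day 182 from PTC; the order of events does not. The conclusion also assumes that resection removes every treated lesion, as the schema's wording implies.

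It would be wrong to infer that the trial's main result is at risk. The primary histologic endpoint, the sample size of 10, the precision figures in 9.2 and the pre-operative CT-pathology comparison are untouched. The effect is confined to secondary summaries, but it changes what may be concluded from them, and the remedy is cheap enough that it should be made.

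**What to change.** Amend the wording of Section 9.3, with a matching line in 7.2:

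1. State that month-6 PET and CT in resected patients are post-surgical long-term follow-up, as in Section 5.0, and are excluded from the SUV and RR summaries of PTC effect.
2. Report baseline SUVmean and SUVmax descriptively.
3. List the month-6 scans of any treated but unresected patient separately.
4. State that RR is computed on the pre-resection CT, in line with Sections 1.0, 2.0 and 7.0.

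As a separate item, the 2-60 day window, the 12-week limit and note I should be reconciled with one another.

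The cost is wording only: no new scans, readers or patients. The plan gives up month-6 SUV and response figures in resected patients as measures of PTC effect, a use they could not have supported.

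### The SAE limits in section 9.4 (0.303, 0.268, 0.327) are not the one-sided 80% limits they are labelled as, and the flag built on them is described inconsistently

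*Combined protocol and SAP*

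**What the plan says.** Section 9.4 first sets out what is expected: "up to 20% of patients may have such complications, but that would not be regarded as reason to stop the study". It then describes a monitoring plan based on a one-sided upper 80% confidence limit, used to find "the first opportunity at which the observed SAE rate provides evidence that the true (and unknown) SAE rate could be > 30" per cent.

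Three limits are given.

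- **0.268**, in a sentence about nine patients that begins "if 1 patient in the first 9 patients are treated and none have an SAE". The text says nine is the smallest sample size at which the limit is still below 30%.
- **0.303**: "The first statistically-based early stopping opportunity for safety reasons occurs if 1 patient has an SAE among the first 8 (or fewer) patients treated".
- **0.327**: "The second such early stopping opportunity for safety reasons occurs if 2 patients have an SAE among the first 10 (or fewer) patients treated".

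Table 1 repeats the last two and gives the consequence differently: "We would recommend re-evaluation of the study for safety reasons if there were X many" SAEs among the first N or fewer patients treated. Its notes add "X = the cumulative number of SAE's observed thus far" and "UCL = the exact 1-sided upper 80% binomial confidence limit for p". No probabilities of triggering are stated. Section 9.5 says that 12-15 patients may have to be enrolled to obtain 10 evaluable ones.

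**The concern.** A limit labelled exact, one-sided and 80% can be checked directly, and these do not check. The investigators and the DSMC will read the limits as carrying 80% one-sided confidence when they carry less.

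The description of the flag is also unsettled. The text presents a trigger as evidence about a rate above 30% and as an opportunity to stop early. Table 1 presents the same trigger as a prompt to re-evaluate. The nine-patient sentence has both one SAE and no SAE. The text counts patients with an SAE, while Table 1 counts SAEs, so one patient with two events could meet row 2 on one reading and not on the other.

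At stake is what a flag means when it is raised and what should follow. The histologic endpoint is not at stake.

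**Working it through.** **1. Confidence carried by the stated limits.** For x patients with an SAE among n, the one-sided confidence of an upper limit U is 1 − P(X ≤ x | n, U). The inputs are the counts and limits in section 9.4.

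- 1/8 at 0.303: 1 − (0.697^8 + 8·0.303·0.697^7) = 1 − (0.0557 + 0.1937) = 0.751.
- 1/9 at 0.268: 1 − (0.732^9 + 9·0.268·0.732^8) = 1 − (0.0603 + 0.1988) = 0.741.
- 2/10 at 0.327: 1 − (0.0191 + 0.0926 + 0.2025) = 0.686.

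None reaches 0.80.

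**2. Which method gives these figures.** The one-sided 80% Clopper-Pearson limit is the 0.80 quantile of Beta(x+1, n−x). The Blyth-Still-Casella interval is exact but not equal-tailed, so the upper end of its two-sided 60% version is not a one-sided 80% limit.

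| SAEs/N | Stated | Clopper-Pearson, one-sided 80% | Blyth-Still-Casella, two-sided 60%, upper end |
|---|---|---|---|
| 1/8 | 0.303 | 0.330 | 0.303 |
| 1/9 | 0.268 | 0.298 | 0.268 |
| 2/10 | 0.327 | 0.381 | 0.327 |
| 2/11 | not given | 0.350 | 0.295 |

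The last column reproduces all three stated values, and it explains why row 2 ends at 10. The plan does not name its method, so this is a match and not proof of origin. It does suggest consistent limits under the wrong label rather than misprints.

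**3. Effect on the triggers.** With Clopper-Pearson, 1/8 (0.330) is still above 0.30 and 1/9 (0.298) still below it, so row 1 still ends at N=8. Row 2 still holds at N=10. It then continues: 0.350 at 11, 0.324 at 12, 0.301 at 13 and 0.281 at 14. Under the labelled criterion, row 2 therefore runs to N=13.

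**4. The nine-patient sentence.** With no SAE, the Clopper-Pearson limit is 1 − 0.2^(1/n): 0.331 at n=4, 0.275 at n=5 and 0.164 at n=9. It is below 0.30 from n=5 (from n=3 by Blyth-Still-Casella, 0.287). Nine is the smallest n only with one SAE, and 0.268 fits 1/9.

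**5. What an upper limit above 0.30 shows.** It shows that 30% is not excluded. The one-sided 80% Clopper-Pearson lower limits at the two triggers are 0.028 (1/8) and 0.083 (2/10), so neither result is evidence that the rate exceeds 30%.

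**6. How often the flag fires.** Assume a check after each of the first 10 treated patients, independent patients with a common SAE rate p, and each patient counted at most once. Table 1 stays silent only if none of the first 8 has an SAE and patients 9 and 10 do not both have one:

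P(fire by 10) = 1 − (1−p)^8 · (1−p²)

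At p = 0.20 this is 1 − 0.1678 × 0.96 = 0.839. With row 2 carried to N=13:

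P(fire by 13) = 1 − (1−p)^8 · [(1−p)^5 + 5p(1−p)^4]

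| True SAE rate | 5% | 10% | 15% | 20% | 30% |
|---|---|---|---|---|---|
| Table 1 as printed, by patient 10 | 0.34 | 0.57 | 0.73 | 0.84 | 0.95 |
| Row 2 to N=13, by patient 13 | 0.35 | 0.60 | 0.77 | 0.88 | 0.97 |

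The chance of firing at 30% relative to 20% is 0.948/0.839 = 1.13. Relative to 10% it is 0.948/0.574 = 1.65, and relative to 5% it is 0.948/0.338 = 2.80.

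**The case against.** The strongest defence is that this is an advisory flag in a 10-patient pilot and that its sensitivity is deliberate. Section 9.4 says the investigators would consider stopping on early examples, Table 1 only recommends re-evaluation, and section 10.0 already provides monthly review of adverse events for all patients with a monthly report to the DSMC. A sensitive flag is a legitimate choice. That stands, and it limits the severity.

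The label error changes no trigger within the first 10 patients, which also stands. The N=13 row matters only if more than 10 patients are treated. Section 9.5 makes that possible, but it speaks of enrolment and does not say that every extra patient will be treated.

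A reader might infer that the plan will probably stop the trial at a rate it calls tolerable, with probability 0.84. The documents do not support that. The 0.84 is the chance of an advisory review, and it applies to the tolerated rate only if the 20% is an SAE rate. The text says such complications, just after a sentence on SAEs, while section 6.0 gives about 15% for pneumothorax alone without restricting it to serious cases. Either reading is possible. If the true SAE rate is 5% or 10%, the flag separates it from 30% noticeably better.

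A reader might also infer that the logic of the rule is reversed. That goes too far: the text says the rate could be above 30%, which is a statement of non-exclusion, and Table 1 starts at one SAE, so it does not flag zero events. What remains is the language of evidence and early stopping around it.

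**Conclusion.** The point holds, at a severity of minor to should-fix. All three stated limits are mislabelled: their one-sided confidence is 0.69 to 0.75 instead of 0.80, and the labelled limits are higher by 0.027 (1/8), 0.030 (1/9) and 0.054 (2/10). The nine-patient sentence is wrong as written, though its conclusion at one SAE in nine survives under Clopper-Pearson (0.298). The wording for the same triggers needs reconciling, and the unit of X needs defining.

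Poor discrimination is a conditional finding. It applies if the tolerated 20% is an SAE rate, which the text does not settle. The firing probabilities rest on the assumptions in step 6 of the working. Nothing here affects the estimate of the success rate, its precision or the target of 10 evaluable patients.

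**What to change.** - **Limits.** Either restate them as one-sided 80% Clopper-Pearson (0.330 for 1/8, 0.298 for 1/9, 0.381 for 2/10) and note that the same criterion carries row 2 to N=13, or name the interval method used and drop the one-sided 80% label.
- **Nine-patient sentence.** Correct it to one SAE among the first nine patients treated.
- **Unit.** Define X as the number of patients with at least one SAE.
- **Meaning.** Describe Table 1 throughout as a review flag, meaning that an SAE rate above 30% has not been excluded, and replace the evidence wording.
- **Operating characteristics.** Add one line with the firing probabilities: 0.34, 0.57, 0.73, 0.84 and 0.95 at 5%, 10%, 15%, 20% and 30% over 10 patients. If row 2 is extended, give the figures to patient 13 as well.
- **Reconcile.** Say whether the 20% refers to SAEs, and bring the stopping and re-evaluation passages into agreement. Any stopping boundary is for the sponsor and the DSMC to choose.

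The cost is a few sentences and one line of probabilities in section 9.4. If the method is named, the printed triggers stay. If the limits are restated, Table 1's limits change and row 2 extends from N=10 to N=13. Sample size and procedures do not change. The drawback is that the plan would openly describe a sensitive flag that may discriminate little at this sample size.

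### The SAE limits in Section 9.4 and Table 1 are labelled one-sided 80% but carry only 69–75% confidence, and the sentence on nine patients contradicts itself

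*Combined protocol and SAP*

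**What the plan says.** Section 9.4 bases SAE monitoring on a one-sided upper 80% confidence limit compared with a true rate of 30%. The legend to Table 1 fixes the type of limit: "UCL = the exact 1-sided upper 80% binomial confidence limit for p".

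Three limits are printed.

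- 1 SAE among the first 8 patients, in the text and in Table 1: "the 1-sided upper 80% confidence limit (0.303) just exceeds 0.30".
- 2 SAEs among the first 10, in the text and in Table 1: "the 1-sided upper 80% confidence limit (0.327) just exceeds 0.30".
- Nine patients, in the text only. The condition is "if 1 patient in the first 9 patients are treated and none have an SAE", and the plan then claims 80% confidence that the true rate is below 30%, "because that is the smallest sample size for which the 1-sided upper 80% CL (0.268) is still < 30" per cent.

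Table 1 is offered as a basis for recommending re-evaluation of the study. It is introduced with "Over the full range of the 10 patients intended for this pilot protocol study".

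**The concern.** An exact one-sided upper 80% limit is a single number for each count and sample size, so the printed values can be checked directly. All three fall below it, by more than rounding can explain.

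The direction matters. The limits are the stated statistical basis of the safety rule, and a limit that is too low makes the SAE rate look better bounded than it is. A reader of Table 1 would take 2 SAEs in 10 to be barely above the 30% line, when at the stated confidence it lies well above.

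The sentence on nine patients is a separate fault. One patient with an SAE and no patient with an SAE cannot both be the condition, and the reader cannot tell from the sentence which count supports the claim.

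**Working it through.** **Inputs, all from Section 9.4 and Table 1.** Confidence 80%, one-sided upper; threshold 0.30; counts 1/8, 2/10 and the nine-patient case; printed limits 0.303, 0.327 and 0.268.

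**Exact limit.** For x events in n patients, U solves P(X ≤ x | n, U) = 0.20. Equivalently, U is the 0.80 quantile of a Beta(x + 1, n − x) distribution.

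**Confidence carried by a printed limit u.** This is 1 − P(X ≤ x | n, u).

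- 1/8 at 0.303: P(X ≤ 1) = 0.697^8 + 8 × 0.303 × 0.697^7 = 0.0557 + 0.1937 = 0.2494, so confidence is 75.1%.
- 1/9 at 0.268: P(X ≤ 1) = 0.732^9 + 9 × 0.268 × 0.732^8 = 0.0603 + 0.1988 = 0.2592 (unrounded sum), so confidence is 74.1%.
- 2/10 at 0.327: P(X ≤ 2) = 0.0191 + 0.0926 + 0.2025 = 0.3142, so confidence is 68.6%.

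| SAEs / patients | Printed | Exact | Understated by | Confidence of printed value | Short of 80% by |
|---|---|---|---|---|---|
| 1/8 | 0.303 | 0.330 | 0.027 | 75.1% | 4.9 points |
| 1/9 | 0.268 | 0.298 | 0.030 | 74.1% | 5.9 points |
| 2/10 | 0.327 | 0.381 | 0.054 | 68.6% | 11.4 points |

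**Can the printed figures be reproduced another way?** One-sided 80% limits by other common methods do not give the set:

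| Method | 1/8 | 1/9 | 2/10 |
|---|---|---|---|
| Printed | 0.303 | 0.268 | 0.327 |
| Wilson | 0.255 | 0.229 | 0.325 |
| Jeffreys | 0.259 | 0.233 | 0.327 |
| Mid-P | 0.270 | 0.243 | 0.334 |
| Upper end of a two-sided 60% Blyth-Still-Casella interval | 0.3034 | 0.2676 | 0.3269 |

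Only the last row matches all three. That interval guarantees 60% two-sided coverage but need not leave 20% in the upper tail, so its upper end is not a one-sided 80% limit.

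**The sentence on nine patients.** With no SAE, the exact limit is 1 − 0.20^(1/n).

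- n = 4: 0.331. n = 5: 0.275. n = 9: 0.164.
- With no SAE, therefore, the figure for nine patients would be 0.164, and the smallest sample size with a limit below 0.30 would be 5.
- With one SAE, the exact limit is 0.330 at n = 8 and 0.298 at n = 9, so 9 is the smallest sample size below 0.30.
- The printed 0.268 matches 1/9 in the Blyth-Still-Casella row. Read literally as 0/9, it would carry 94% confidence.

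Both the figure and the reason given therefore belong to one SAE in nine.

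**Effect on the triggers.** With either set of limits, 1/8 and 2/10 exceed 0.30 and 1/9 does not. The margins change: 2/10 exceeds 0.30 by 0.081 rather than 0.027, 1/8 by 0.030 rather than 0.003, and 1/9 clears it by 0.002 rather than 0.032.

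**The case against.** The best defence has two parts.

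First, the figures are not arbitrary. They come from a recognised exact method, the two-sided 60% Blyth-Still-Casella interval, so one could correct the label and leave the numbers. The explanation of their source is convincing. As a cure it falls short: the text would still claim 80% one-sided confidence on the printed 0.268, which carries 74.1%. Relabelling would also mean abandoning the one-sided 80% criterion on which Section 9.4 says the rule rests.

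Second, nothing operational changes. The working part of Table 1 is the pair of counts, those counts stay the same, and they lead only to a recommendation to re-evaluate. Section 10 adds monthly review and a monthly report to the data and safety monitoring committee. The conclusion for nine patients, a rate below 30% with 80% confidence, is also true for both 0/9 and 1/9. All of this stands, and it limits the weight of the point. It does not make the printed limits or the contradictory sentence correct.

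**Conclusion.** The concern holds. The three printed limits are not exact one-sided upper 80% binomial limits. They understate those limits by 0.027 to 0.054 and carry 68.6% to 75.1% confidence. The sentence on nine patients contradicts itself, and its figure and its reasoning fit only one SAE in nine.

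The 69–75% range assumes that 0.268 refers to 1/9, which the matching interval and the smallest-sample-size argument both support. The binomial model takes patients as independent, with at most one counted SAE each.

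The consequence is misreported uncertainty in a safety rule, in the favourable direction. No decision within the first 10 treated patients changes. It should be corrected because the limits are wrong as labelled and the correction is easy.

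**What to change.** In Section 9.4 and Table 1:

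- Replace 0.303 with 0.330 and 0.327 with 0.381, each in the text and in the table.
- Name the method in the legend: exact one-sided Clopper-Pearson.
- Delete the word just for 2/10. Deleting it for 1/8 as well would be consistent.
- Reword the sentence on nine patients along these lines: if 1 of the first 9 patients treated has an SAE, the one-sided upper 80% limit is 0.298, and 9 is the smallest number of patients with one SAE for which it is below 0.30.

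The cost is three figures in five places, a method name, a deleted word or two and one sentence. Neither trigger nor the sample size is touched. The only downside is that the stated limits become less favourable.

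A separate question, not part of this correction, is whether Table 1 is meant to apply after the tenth treated patient. Its legend counts "N = the number of cryotherapy patients treated thus far" and the table ends at 10, while Section 7.5 replaces inevaluable patients and Section 9.5 foresees enrolling 12–15. The choice of method would matter there: for 2 SAEs in 11 the exact limit is 0.350, and the Blyth-Still-Casella value is 0.295. The sponsor should state the intended scope and reconcile it with the remark "we anticipate that up to 20% of patients may have such complications, but that would not be regarded as reason to stop the study".
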